#### **Cognitive tasks:**

**Stop Signal Task** - A task assessing impulse control and attention. Participants respond as quickly as they can to directional arrows by pressing computer keys. Some of the arrows are accompanied by an auditory tone indicating that the participant should not respond to that arrow. 9 minutes (Verbruggen et al. 2019; <https://www.millisecond.com/download/library/v5/stopsignaltask/stopsignaltask2019/stopsignaltask2019.manual>)

**N-back task (2 and 3 back)** - A task assessing working memory and information manipulation. Participants are shown a sequence of shapes and asked to respond to shapes that they've seen previously. 9 minutes (Jaeggi et al., 2010; <https://www.millisecond.com/download/library/v5/nback/singletasknback/singletasknback.manual>)

**Trail Making Test (Trail a and Trail b)** - A test assessing task-shifting. Participants draw lines connecting numbers and letters together in order. 3 minutes (Reitan, 1955; Tombaugh, 2004; <http://apps.usd.edu/coglab/schieber/psyc423/pdf/IowaTrailMaking.pdf>)

\*Note, while training effects may occur on the cognitive tasks, this will be accounted for in the analyses. If there is an effect of NAC, it should lead to improvements greater than placebo. Recent estimates of the stop signal task and N-back task indicate fair to good reliability (~.5-.7) (Enkavi et al., 2019). However, a recent optimization of the Stop Signal Task is expected to improve reliability (Verbruggen et al., 2019). Likewise, a meta-analysis found good test-retest reliability (~.7) of the trail making test (Calamia et al., 2010).

Assessment	Screening: Phone Call	Baseline Visit (Wk 0)	In-person Visit 1 (W1)	Phone Call 1 (W2)	In-person Visit 2 (W3)	Phone Call 3 (W4)	In-person Visit 3 (W5)	Phone Call 4 (W6)	Post-treatment visit (W7)
Physical Exam		x							
Informed Consent Form		x							
Inclusion /Exclusion Criteria	x								
Enrollment /Randomization		x							

Self-report							
Demographics	x						
ASSIST	x						
AUDIT	x						
APT		x	x	x	x		x
PACS	x	x	x	x	x		x
DDT	x	x	x	x	x		x
SIAS-6 and SPS-6	x	x	x	x	x		x
TLFB		x	x	x	x	x	x
E-cigarette questions	x						
HONC	x						
GAD-7	x	x	x	x	x		x
AUQ				x			
Mental health services		x					
Medications and supplements		x					
Treatment guess						x	
Military service questions	x						
Interview							
SCID-5 AUD	x						
Breathalyzer	x	x	x	x	x		x
Temperature screen	x	x	x	x	x		x
COVID screen	x	x	x	x	x		x
Pill counts		x	x	x	x		x
MADRS	x	x	x	x	x		x
ACR				x			
SAFTEE		x	x	x	x		x
Have you experienced any new or worsening side effects?			x	x	x		
Treatment questions and personalized recommendations	x	x	x	x	x		x
Computer Tasks							
Stop Signal	x	x	x	x	x		x
N-back task	x	x	x	x	x		x
Trail Making task	x	x	x	x	x		x

**10.3 At any point in the study, will you request, use, or access health information in any form, including verbal, hard copy and electronic?**

Yes  No

**11.0 Statistical/Data Analysis Plan**

**11.1 Statistical Considerations:**

List the statistical methods to be used to address the primary and secondary objectives, specific aims, and/or research hypotheses. Explain how missing data and outliers will be handled in the analysis. The analysis plan should be consistent with the study objectives. Include any sub-

group analyses (e.g., gender or age group). Specify statistical methods and variables for each analysis. Describe how confounding variables will be controlled in the data analysis

Independent samples t-tests will be used to evaluate for differences in dropout rate and total adverse events between study groups.

For our exploratory aims, we will assess the treatment effects on variables of interest using linear mixed models. Given the exploratory nature of analysis, we will report both false discovery rate corrected and nominally significant findings. See 11.6 for more detail on planned analyses.

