Participants with a BAC of 0 will complete the informed consent process. They will undergo a physical exam by the physician. During the physical, female participants will undergo a pregnancy screen using a pregnancy test kit. If the screen is positive, they will be told they are not eligible to participate and they will not be counted in the study's enrollment number. Further, they will be instructed to contact their primary care provider to confirm the results and discuss the risks of alcohol use during pregnancy. Next, the RA will conduct the MADRS interview, then participants will complete the TLFB self-report form. They will then complete the computer questionnaires (demographics, ASSIST, AUDIT, APT, PACS, DDT, SIAS-6, SPS-6, e-cigarette questions, HONC, GAD-7, mental health services, medications and supplements, and military service questions) and behavioral tasks (Stop Signal, N-back, and Trail Making). Participants will be asked the treatment questions and referred to mental health resources by the RA. They will then be scheduled for their next study session and complete payment paperwork with the RA. Then they will be randomized to either 7 weeks of oral NAC (3000 milligrams) or 7 weeks of placebo. We will advise participants to inform their provider of participating in this research study and of taking 3000mg NAC or placebo. Participants will be given a business card to give to their provider stating they are in the study and taking 3000mg of NAC or placebo. Participants will be instructed to go to the Investigational Pharmacy (building 9) immediately after their appointment to pick up their study medication. They will be escorted by the RA if they have never been before or don't remember how to get there. The pharmacy will handle gender stratified randomization. The first study session will take approximately 3 hrs to complete.

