#### In-person visits (Wk 1, 3, and 5)

Participants will be temperature checked with a non-contact thermometer and screened for COVID symptoms. If their temperature is 100.4°F and above or they endorse any of the COVID symptoms, they will be rescheduled and told to get tested for COVID and see their primary care provider. Participants will be administered a breathalyzer by the research assistant (RA) to check BAC. If BAC is > 0, the RA will wait a few minutes and readminister. If BAC is 0, the RA will proceed with the study. If BAC is between .01 and .049, the RA will have the participant wait until it drops to 0. If the participant refuses to wait, the research team will reschedule their appointment and the participant can leave. If BAC is  $\geq .05$ , the participant will be transported to the WRNMMC emergency department to assess alcohol withdrawal. If the participant refuses to go to the emergency department, they will be informed that the research team will be forced to contact the NSA Bethesda police ([contact]) out of concern for their safety. A member of the study team will walk the participants unless by the judgement of the research assistant, the participant is unable to walk unassisted. In this case, we will contact 911 to dispatch a team to evaluate the participant and transport them as needed to the WRNMMC ED.

Female participants will be asked by the physician if they believe there's been a change to their pregnancy status since their last appointment. If they believe there has been a change, they will undergo a pregnancy screen using a pregnancy test kit, administered by the physician. If the screen is positive, they will be told they are no longer eligible to participate. Further, they will be instructed to contact their primary care provider to confirm the results and discuss the risks of alcohol use during pregnancy. The physician will then assess the participant for adverse events with the SAFTEE.

Next, the RA will conduct the pill counts, MADRS interview, then participants will complete the TLFB self-report form. Participants will then complete the computer questionnaires (APT, PACS, DDT, SIAS-6, SPS-6, and GAD-7) and behavioral tasks (Stop Signal, N-back, and Trail Making). These study sessions will take approximately 2 hrs to complete.

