### Interview:

- **SCID-5 AUD:** Semi-structured diagnostic interview for alcohol use disorder. (First, Williams, Karg, & Spitzer, 2015)
- **Physical exam:** completed by a physician who is an associate investigator on the study.

- **Pregnancy screen:** completed by a physician who is an associate investigator on the study. The Quidel QuickVue hCG Urine kit will be used.
- **COVID screen:** Participants will be screened for possible COVID symptoms and exposure.
- **Temperature screen:** Participants will be temperature checked with a non-contact thermometer.
- **Breathalyzer:** at each in-person appointment, we will assess BAC with a breathalyzer in compliance with the Department of Transportation (DOT)/National Highway Traffic Safety Administration (NHTSA).
- **Pill count and diary:** At each clinic visit, pill counts will be derived from returned pill bottles to determine intake and compare with the medication diaries that the participant is asked to fill out. (Lam et al., 2015)
- **Montgomery-Åsberg Depression Rating Scale (MADRS):** 10-item questionnaire assessing depression symptoms. (Williams & Kobak, 2008)
- **Alcohol Cue Reactivity (ACR):** a task in which the participant is exposed to stimuli associated with alcohol (Rohsenow et al., 2000). This task will be conducted with a virtual reality bar lab using the Oculus rift headset (<https://www.oculus.com/rift-s/>) and software from In Virtuo (<http://invirtuo.com/en/>). Please note that the cue reactivity software from In Virtuo is not directly displayed on their website, but is an adaptation of the PTSD bar scenario (<http://invirtuo.com/en/software/software/>).
- **Systematic Assessment for Treatment Emergent Effects (SAFTEE):** The SAFTEE is a systematic assessment of side effects for clinical trials. Participants are first asked about side effects in an open-ended way and then asked specifically about side effects that frequently occur. This measure takes approximately 5-10 minutes to complete. (Johnson, Ait-Daoud, & Roache, 2005)
  - **Note:** For phone sessions, the study staff will not administer the SAFTEE but rather ask the open-ended question, have you experienced any new or worsening side effects? Would you like to speak with the team physician prior to your appointment in one week?

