**14.0 Risks and Benefits**

**14.1 Risks of Harm:**

Identify all research-related risks of harm to which the subject will be exposed for each research procedure or intervention as a result of participation in this study. Consider the risks of breach of confidentiality, psychological, legal, social, and economic risks as well as physical risks. Do not describe risks from standard care procedures; only describe risks from procedures done for research purposes

Side effects of NAC are uncommon and relatively minor. The most frequently reported side effects are nausea, vomiting, and diarrhea. They often occur at identical rates to placebo. Rarely and primarily with intravenous administration, anaphylactic reactions may occur and can consist of rash, pruritus, angioedema, bronchospasm, tachycardia, and blood pressure dysregulation. Finally, given the limited reports on NAC in pregnant and lactating women, it should not be used in this population in the context of research and thus this is an exclusion criteria.

Sources: 1) FDA approved acetylcysteine labels (<https://dailymed.nlm.nih.gov/dailymed/index.cfm>)

Data collection may risk loss of privacy.

There is a risk of alcohol withdrawal.

There are legal risks if the participant enters the base intoxicated and/or the NSAB police are called.

There is a chance that participants could experience side effects such as nausea, motion sickness, eye strain, or seizures while completing the virtual reality-based assessment. Symptoms of virtual reality exposure can persist and become more apparent hours after use. These symptoms may put participants at an increased risk of injury when engaging in normal activities such as driving, operating machinery, or engaging in other demanding activities.

For military personnel, there is a risk that their command could be informed of their intoxication by the emergency department if the participant is transported there for alcohol withdrawal.

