### **Expected Adverse Events (EAEs)**

The primary EAEs for the study will be potential medication side effects.

Side effects are uncommon and relatively minor. The most frequently reported side effects are nausea, vomiting, and diarrhea. They often occur at identical rates to placebo. Rarely and primarily with intravenous administration, anaphylactic reactions may occur and can consist of rash, pruritus, angioedema, bronchospasm, tachycardia, and blood pressure dysregulation. Finally, given the limited reports on NAC in pregnant and lactating women, it should not be used in this population in the context of research and thus this is an exclusion criteria.

Sources: 1) FDA approved acetylcysteine labels (<https://dailymed.nlm.nih.gov/dailymed/index.cfm>)

To assess them, the study physician will use the Systematic Assessment for Treatment Emergent Events (SAFTEE) interview at each in-person appointment. This includes asking about common symptom indicators as well as an "other" option to record other side effects:

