#### ABDOMINAL PAIN

*Minimal:* Single occurrence of abdominal pain that is not distressing and does not limit activities

*Mild:* Multiple occurrences of abdominal pain that is not distressing and does not limit activities

*Moderate:* Single or multiple occurrences of abdominal pain that causes distress but does not limit activities

*Severe:* Abdominal pain or cramping of sufficient severity to limit activities

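### The only planned between-arm safety analysis is a t-test on an undefined adverse-event total, which can mask a difference in nausea, vomiting or diarrhea; add per-arm incidence with intervals

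*Combined protocol and SAP*

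**What the plan says.** Section 11.1 (Statistical Considerations) states: "Independent samples t-tests will be used to evaluate for differences in dropout rate and total adverse events between study groups". It does not say what is counted: events, people or symptom-visits, from what grade upward, and with or without reports made by phone. Section 11.6 covers drinking, craving, cognition, mood, marijuana and cigarettes, and does not mention adverse events. Section 16.1 covers reporting to the IRB and FDA, clinical follow-up and pausing, but no summary by arm.

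The data themselves are detailed. At the in-person visits (Section 10.1), "The physician will then assess the participant for adverse events with the SAFTEE". Section 16.1 lists 16 graded symptoms and an "option to record other side effects". On the phone weeks the SAFTEE is replaced by an open question, "have you experienced any new or worsening side effects" (Section 10.2). The baseline steps in Section 10.1 include an examination, "They will undergo a physical exam by the physician", but no SAFTEE.

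On what to expect, Section 14.1 says: "The most frequently reported side effects are nausea, vomiting, and diarrhea". Sections 14.1 and 16.1 both add: "They often occur at identical rates to placebo". Neither gives a rate.

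**The concern.** A mean difference in a mixed count does not show how many people in each arm had the side effects that the protocol itself expects. It also combines things that can move apart. Three of the 16 items are the named gastrointestinal ones. Others, such as libido change or missed menses, have no evident link to them. Two more, nervousness/anxiety and depression, measure what Section 9.3 hypothesizes NAC will improve. A gastrointestinal excess could be diluted by the unrelated items and partly cancelled by an improvement in the mood items.

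At stake is the usefulness of the trial's one stated safety comparison. As written it cannot test the protocol's own statement that these effects often match placebo. It also leaves later readers a p-value on an undefined sum, not an incidence that they could combine with other studies.

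**Working it through.** **Inputs.** From the documents: 25 per arm (Section 11.4), which is 40 + 10 for dropout = 50 in total (Section 11.5); 16 SAFTEE items plus the free category (Section 16.1); three named gastrointestinal (GI) items. The plan states no figure for safety, so there is none to reproduce. Assumed: two-sided 0.05, one count per person per item, the free category left out, and all symptom rates.

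**1. The total does not identify the pattern.** A rise of 25 points on each of 3 items gives 3 × 0.25 = 0.75 events per person. A rise of 5 points on each of 15 items gives 15 × 0.05 = 0.75. The planned contrast is the same.

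**2. Cancellation.** Suppose NAC raises each GI item by 5 points and lowers the anxiety and depression items by 7.5 points each. The net difference is 3 × 0.05 − 2 × 0.075 = 0. With GI rises of 25 points and mood falls of 10 points, it is 0.75 − 0.20 = 0.55.

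**3. Dilution by hand.** Take independent items, each GI item at 15% on placebo and 40% on NAC, and the other 13 at 10% in both arms. For a sum, variance = Σp(1 − p) and SE = √[(V₀ + V₁)/25].
- Total: V₀ = 3(0.15)(0.85) + 13(0.10)(0.90) = 0.3825 + 1.17 = 1.5525. V₁ = 3(0.40)(0.60) + 1.17 = 1.89. SE = √(3.4425/25) = 0.371. Difference/SE = 0.75/0.371 = 2.02. Power is about 51%.
- GI count alone: SE = √[(0.3825 + 0.72)/25] = 0.21. Difference/SE = 0.75/0.21 = 3.57. Power is about 94%.

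(Power is from the noncentral t distribution with 48 degrees of freedom.)

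**4. Dilution over a range.** A simulation of 16 binary items (25 per arm, 6,000 runs per setting) varied three things: other items at 3–5%, 10% or 15–30%; the mood items at 10%, 20% or 40%, equal in both arms; and person-level clustering (logit SD 0, 0.5 or 1.0). Missed menses was possible only in women, assumed to be 30%. Abdominal pain and appetite change either stayed with the other items or moved with the GI items. With no arm difference, both tests rejected in 4.4% to 5.6% of runs.

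| Each GI item, placebo vs NAC | Total, only GI items differ | Total, pain and appetite differ too | 3-item GI count |
|---|---|---|---|
| (a) 15% vs 40% | 14–69% | 31–95% | 86–94% |
| (b) 15% vs 30% | 8.5–33% | 14.5–61% | 48–60% |
| (c) 15% vs 20% | 5–8% | 6–13% | 10–13% |
| (d) 5% vs 10% | 5–10% | 6–15.5% | 17–22% |
| (e) 5% vs 20% | 9–39% | 16–73% | 72–83% |

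In the cases most favorable to the total (no clustering, linked items moving, other items at 4%), its power matches the GI count: 95% vs 94% in (a), 61% vs 59% in (b), 12% vs 12% in (c). The mood items were held equal throughout, so the table does not include the cancellation in step 2.

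**5. What an incidence table would give.** Intervals are Clopper-Pearson per arm, and exact unconditional (inverting the score test) for the difference.
- 10/25 in each arm: 40% (21 to 61%); difference 0 points (−26 to +26).
- 3/25 in each arm: 12% (3 to 31%); difference 0 (−21 to +21).
- 9/25 vs 3/25: difference +24 (0 to +47).
- 8/20 in each arm, at the 20 per arm of Section 11.5: difference 0 (−29 to +29).

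**The case against.** Safety is not among the aims in Section 9.3, and the field in Section 11.1 asks for methods tied to aims and hypotheses. Leaving a descriptive table out of that field is weak evidence that none will be made. That stands, and it limits the weight of the point.

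Summing the SAFTEE items is a reading and not a stated rule. A severity threshold, an attribution rule or repeat counting could each change the total. That also stands: the simulation models one plausible rule.

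The dilution figures rest on assumed rates. Where side effects are uncommon and related symptoms such as abdominal pain (whose lowest grade is "Single occurrence of abdominal pain that is not distressing and does not limit activities") move with the GI items, the total may lose almost nothing. Scenarios (a) and (e) assume excesses of 15 to 25 points per item, which fit poorly with rates near placebo. Scenario (c) implies 1 − 0.85³ = 39% of placebo participants with a GI event if items are independent, which is hardly uncommon. These points stand too, and they are why the case is for estimates and not for a better-powered test.

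A reader might infer that the trial will be unable to report GI rates by arm, or that participants are less well protected. The documents support neither. Symptoms are recorded and graded item by item, so the rates can be tabulated after unblinding. Section 16.1 covers individual events, follow-up and pausing without relying on this test.

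What does not stand is that the choice is harmless. The plan names a specific method, and that method can give a less informative answer than data already scheduled for collection would allow.

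**Conclusion.** The point holds as a modest reporting improvement. The sole between-arm safety analysis uses an undefined total which, if it sums the SAFTEE items, can mask an excess of nausea, vomiting or diarrhea by dilution and by offset from the mood items. Under assumed rates the loss of power runs from large (14% against at least 86% in scenario (a)) to about zero. If rates are close to placebo, as in (c) and (d), neither test exceeds 22% and only estimates are useful.

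That the total cannot show per-arm incidence needs no assumed rate. That it sums all SAFTEE items is the natural reading of Section 11.1, and the offset also assumes that the mood benefit predicted in Section 9.3 would appear in the SAFTEE anxiety and depression items. It would go too far to conclude that the total will hide a GI effect, or that the t-test must be removed: the documents give no symptom rates, and a descriptive summary can sit beside the test.

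**What to change.** In Section 11.1:

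- Make the main safety summary the number and percentage per arm with at least one nausea, vomiting or diarrhea event after starting study medication. Give exact 95% intervals per arm and for the difference, with participants who had at least one adverse-event assessment after starting medication as the denominator.
- Add a descriptive table of every SAFTEE item and the free category by arm and worst grade, with women as the denominator for missed menses and phone-only reports shown as ungraded.
- Keep the total as a secondary line with its rule stated: one count per person per item, visits and phone reports combined.

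The cost is a few lines of text and one table from assessments already scheduled. There are no extra visits, participants or tests. Because no baseline SAFTEE is listed, symptoms present before treatment cannot be separated unless the form records onset. If it does not, either add one tick per symptom or count all symptoms reported after starting medication. The downside is imprecision: about plus or minus 21 to 26 points for the difference at 25 per arm when the arms are equal, so the table is descriptive only.

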## 11.2 Sample Size:

50

## 11.3 Total number of subjects requested (including records and specimens):

50

## 11.4 If you are recruiting by study arm, please identify the arms of the study and how many subjects will be enrolled in each arm

Arm 1: n-acetylcysteine. 25 participants randomly selected

Arm 2: placebo. 25 participants randomly selected

## 11.5 Please provide a justification for your sample size

**Sample size justification.** The primary aim of the present investigation is to establish feasibility, dropout rate, and the standard deviation of the outcome measures. The latter two are necessary to accurately estimate the sample size of the main trial. We are setting the pilot sample size in order to minimize the total sample size of the pilot and main trial together, recognizing that the pilot trial is part of a larger clinical development program. 40 participants (20 per arm) are needed to generate standard deviations (of the outcome measures) to be used in sample size calculation for the main trial assuming a main trial effect size in the small-to-medium range and power = .8.(Whitehead, Julious, Cooper, & Campbell, 2016) We will include an additional 10 participants to account for dropout, leading to a sample size of 50.

